Clinical signs and symptoms of infection on the target ulcer: Presence or absence of the clinical signs of infection (i.e., redness, swelling, tenderness, heat, purulence) as assessed by the Investigator or confirmed (i.e., microbiological culture) clinical infection, in the target ulcer.

Need for administration of antibiotics: Administration of antibiotics for a target ulcer infection.

Pain on removal of dressing: Subject response to the level of pain as recorded on the VAS during the removal of the NPWT dressing.

Pain on initiation of therapy/during dressing wear: Subject response to the level of pain as recorded on the VAS during the initiation of NPWT therapy (dressing draw-down) and during wear.

Dressing wear time: Time (days) between dressing changes.

Number and reason for dressing changes: Total number of dressing changes over the 12week treatment period and the documented reason for a dressing change.

Closure method: The number of subjects that undergo a surgical intervention (closure by simple flap, Split-Thickness Skin Graft (STSG), delayed primary intention with sutures).

Additional interventions: The number of subjects that require hospital admission, a surgical intervention for a wound related complication, or specialist referral for wound related complication.

Device trouble-shooting: The number and type of device trouble shooting episodes (alarm conditions/device failures/other malfunctions).

Impact of the device on aspects of daily living and satisfaction with device therapy: Subject response to a custom questionnaire to assess the impact of treatment with the device on subject's daily activities and satisfaction with the device.

CONFIDENTIAL DOCUMENT
This document contains confidential information, which is the property of Smith & Nephew, Inc. Do not copy, disclose, or circulate without written authorization from the appropriate Smith & Nephew personnel

SAFETY: Recording of AE associated with the target ulcer and all SAE

PK: NA

Adverse Device Effects:

Both volunteered and elicited

Other:

CONFIDENTIAL DOCUMENT
This document contains confidential information, which is the property of Smith & Nephew, Inc. Do not copy, disclose, or circulate without written authorization from the appropriate Smith & Nephew personnel

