The duration of dressing wear (dressing wear time) will be calculated using the visit date captured on the CRF and, if applicable, the date of additional/unscheduled dressing changes; by subtracting the date of dressing application from the date of dressing removal. The average wear time will then be derived for each subject using the following formulae. Average subject wear time = sum of duration of wear for the subject / number of dressings used by the subject.

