Duration of wear = Date of removal visit – Date of application visit – duration of study therapy interruption

If an unscheduled visit takes place between consecutive assessments multiple duration of wear values will be derived:

Duration of wear 1= Date of unscheduled visit – Date of application study visit

Duration of wear 2= Date of removal study visit – Date of unscheduled visit – duration of study therapy interruption

If more than one unscheduled visit occurs between consecutive assessments, further multiple wear times will be derived as above.

27. The average wear time per patient (patient level) will be derived as follows per subject:

Sum of duration of dressing wear (dressing level) values / Count of duration of dressing wear (dressing level) values

28. The median value for the baseline (Run-In Visit 2/Study Visit 1) target ulcer area will be derived for both the Full Analysis Set and Per Protocol populations by wound type and overall. The median value will also be derived for the depth and volume.

29. Whether or not the reference ulcer is clinically infected at any Study Visit.

30. Whether or not the reference ulcer has signs of infection at any Study Visit.

31. Whether an intervention was required will be derived for each subject:

If an unscheduled visit is recorded, where the reason for intervention is not given as routine: Intervention = Yes

If no unscheduled visits are recorded: Intervention = No

32. Whether prescription of an antibiotic was required will be derived for each subject:

If "have any systemic antibiotics been prescribed" = Yes at any assessment, or any antibiotic medications are recorded on the concomitant medications form, with a start date after randomization: Antibiotic = Yes

Document Number: 1004313

Document Version: 06

Document Part: 000

Document Status: Released

If "have any systemic antibiotics been prescribed" = No at all assessments, and no antibiotic medications are recorded on the concomitant medications form:
Antibiotic = No

33. Whether an intervention or prescription of an antibiotic was required will be derived for each subject:
If Intervention derivation (Derived Variable 31) = Yes or Antibiotic derivation (Derived Variable 32) = Yes, then need for intervention or antibiotic= Yes
If Intervention derivation (Derived Variable 31) = No or Antibiotic derivation (Derived Variable 32) = No, then need for intervention or antibiotic= No

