34. All pain assessments (dressing removal, during wear, on initiation of therapy) will be derived as follows:
In cases where pain = No, the VAS pain value will be coded as 0
35. Level of Exudate (amount) will be coded as follows- In cases where Exudate presence=No, then the level/amount of exudate will be coded as None.
36. The responses to the aspects of the wound assessment tool (BWAT-M); Undermining, Necrotic Tissue Type, Necrotic Tissue Type, Necrotic Tissue Amount, Exudate Type, Exudate Amount, Skin Color Surrounding Wound, Granulation Tissue and Epithelialization will be coded at each study visit as defined in Section 7. The individual coded values will then be summed at each individual study visit to give a total wound status score.
37. The personnel time taken at each Study Visit will be derived as:
No. of personnel applying the dressing x time taken to apply the NPWT system
38. The total personnel time taken at throughout the study will be the sum of the personnel time at Study Visits per subject.
39. The duration for which compression therapy was interrupted at each Study Visit in hours will be derived as: hours + (daysx24). If no interruption is recorded then the number of hours will be coded as 0.

ST:

9 7 5

Reference:

CE/052/PIC

Customer Code:

0 5

40. The duration for which study therapy was interrupted at each Study Visit in hours will be derived as: hours + (daysx24). If no interruption is recorded then the number of hours will be coded as 0.
41. The total duration (in hours) for which compression therapy was interrupted per subject will be calculated as the sum of the interrupted duration at each Study Visit.
42. The total duration (in hours) for which study therapy was interrupted per subject will be calculated as the sum of the interrupted duration at each Study Visit.
43. In cases where the ulcer is recorded as closed in the investigators opinion the following imputations will be made if missing values are present:
- Presence of infection = No
 - Presence of clinical signs of infection = No
 - Level of Exudate = None/No
 - Extent of undermining = None
 - Necrotic tissue present = No
 - Epithelialization at target ulcer = 100% wound covered, surface intact
44. Individual flags for whether each event was a serious adverse event, severe adverse event, investigational device related adverse event, a serious investigational device related adverse event, an unexpected adverse event and a serious unexpected adverse event.

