4.6 Protocol Deviations

The occurrence of the following examples of protocol deviations and significant protocol deviations, and the number of subjects with a protocol deviation and significant protocol deviation will be summarized:

- Patients that do not meet the inclusion/exclusion criteria but are randomized (the reason for failure of inclusion/exclusion criteria will be summarized)
- Subjects with a PICO duration of dressing wear is >7 days where no wound filler is used
- Subjects with an ActiV.A.C.®, or PICO in combination with a wound filler, with a duration of dressing wear >3 days
- Missed Study Visit

- Patients that receive study treatment with NPWT for greater than 85 days (12 weeks allowing +1 day)
- Patients taking a prohibited concomitant medication
- Patients with a serious device related adverse event who are not withdrawn from study treatment
- Attendance of weekly Study Visit outside ± 1 day window
- Failure to complete the Subject Exit survey or Health Related Quality of Life questionnaires (EQ-5D or CWIS) at the required timepoints

Document Number: 1004313

Document Part: 000

Document Version: 06

Document Status: Released

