4.12 Other Data Summaries

Intended method of closure

The intended method of ulcer closure recorded at Study Visit 1 will be cross-tabulated against the actual method of closure recorded for those ulcers that achieve closure, with the remaining ulcers coded as not-closed.

This summary will be repeated including only those wounds that achieved confirmed closure; the remaining ulcer will be coded as not-confirmed closure.

Ulcer Debridement

Whether the target ulcer was debrided, and the type of debridement used, will be summarized by Study Visit and overall. Separately, whether the target ulcer was debrided, and the type of debridement used, will be summarized at Run-In Visit 2.

Interruption of study therapy

Whether the study therapy was interrupted between study visits, and if so, how long for (in hours), will be summarized overall Study Visits by treatment.

Additionally, the total time per subject for which the study therapy was interrupted between study visits will be summarized by treatment.

Interruption of compression therapy

Whether the compression therapy was interrupted between study visits, and if so, how long for (in hours), will be summarized overall Study Visits by treatment.

Additionally, the total time per subject for which the compression therapy was interrupted between study visits will be summarized by treatment.

Resource Use

The dressing applied, kit size used, whether a filler was used, the filler used, will be summarised at each Study Visit and overall. Whether the subject is using any compression therapy or pressure relieving/offloading therapy, and the type of therapy/equipment used will be summarized.

The device therapy mode and pressure setting (continuous), high/low therapy set points and time on/off cycle times (intermittent), and adjustable compression rate will be summarized for ActiV.A.C.® subjects only.

The personnel time taken (in minutes) to apply the NPWT system will be summarized overall Study Visits by treatment, and separated by intermittent/continuous, and by whether any filler dressing was used.

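### SAP 4.3 item 26 subtracts a therapy interruption derived in hours from a wear time in days, and departs from the wear-time definition in protocol 9.4 and SAP 2.3.3

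*SAP*

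**What the plan says.** **Protocol.** The synopsis gives the unit: "Dressing wear time: Time (days) between dressing changes". Section 9.4 gives the calculation: "by subtracting the date of dressing application from the date of dressing removal". There is no interruption term.

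**SAP 2.3.3.** The exploratory endpoint section repeats the protocol calculation, again with no interruption term.

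**SAP 4.3 item 26.** With no unscheduled visit between assessments, the rule is "Duration of wear = Date of removal visit – Date of application visit – duration of study therapy interruption". With one, the dressing removed at the unscheduled visit is a plain date difference, and the following dressing is "Duration of wear 2= Date of removal study visit – Date of unscheduled visit – duration of study therapy interruption". Item 26 states no unit and does not refer to item 40.

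**SAP 4.3 item 40.** "The duration for which study therapy was interrupted at each Study Visit in hours will be derived as: hours + (daysx24" (the quote stops before the closing bracket). If no interruption is recorded, the value is 0. The subject total in item 42 and the summaries in SAP 4.12 are also in hours.

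**Use of the result.** Item 27 averages per subject: "Sum of duration of dressing wear (dressing level) values / Count of duration of dressing wear (dressing level) values". SAP 4.11 fits a linear regression to that average, with treatment as a term. SAP 4.6 lists wear-time deviations in days, for example "Subjects with a PICO duration of dressing wear is >7 days where no wound filler is used", and a limit of more than 3 days for ActiV.A.C. or for PICO with a filler.

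**The concern.** There are two separate faults.

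The first is a unit fault. The only per-visit interruption variable the SAP defines is in hours, and item 26 takes it from a number of days without dividing by 24.

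The second is a definition fault that remains even if a programmer converts the unit. How long a dressing was on the wound and how long therapy ran under it are different quantities. The protocol and SAP 2.3.3 define the former; item 26 computes something nearer the latter. The SAP therefore disagrees with itself as well as with the protocol.

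At stake are the exploratory comparison of wear time between devices, the wear-time summaries, and possibly the wear-time deviation flags.

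**Working it through.** The plan states no wear-time figure, so there is nothing to reproduce. The check compares three versions of the rule.

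**Inputs.** *g* is the gap in days between application and removal. *h* is the recorded interruption in hours. The documents give no expected interruption length, so every *h* below is an assumption chosen for illustration.

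**Formulas.**
- Literal (item 26 with item 40 inserted as it stands): g − h
- Converted: g − h/24
- Protocol 9.4 and SAP 2.3.3: g

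**One dressing, g = 7.**

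| h (assumed) | Literal | Converted | Protocol |
|---|---|---|---|
| 0 | 7 | 7.0 | 7 |
| 3 | 7 − 3 = 4 | 7 − 0.125 = 6.9 | 7 |
| 12 | 7 − 12 = −5 | 7 − 0.5 = 6.5 | 7 |
| 24 | 7 − 24 = −17 | 7 − 1 = 6.0 | 7 |

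The literal value is negative whenever *h* exceeds *g* as plain numbers: above 7 h for a 7-day dressing, above 3 h for a 3-day dressing. With no recorded interruption, all three versions agree.

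**Subject mean (the analysed variable).** Take twelve 7-day dressings, one with an assumed 24 h interruption.
- Literal: (11 × 7 − 17)/12 = 60/12 = 5.00
- Converted: (11 × 7 + 6)/12 = 83/12 = 6.92
- Protocol: 84/12 = 7.00

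**After an unscheduled visit.** Split a 7-day interval into 3 and 4 days, with an assumed 6 h interruption. The second dressing is 4 − 6 = −2 literal, 4 − 0.25 = 3.75 converted, and 4 by the protocol. Item 26 charges the whole interruption to this dressing, whichever dressing was on when therapy stopped.

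**Deviation flags.** An unfilled PICO dressing worn 8 days with an assumed 2 h interruption is 8 − 2 = 6 literal (not above 7), 7.92 converted (flagged) and 8 by the protocol (flagged). Conversion alone does not remove the problem: with 24 h, the converted value is 8 − 1 = 7.00, which is no longer above 7.

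**Whether it cancels between arms.** The literal shift in a subject's mean is total interruption hours divided by number of dressings, so it depends on how often dressings are changed. Protocol 9.1.7 has tNPWT and filler users change dressings at 2–3 days. Assume 84 days and 24 h of interruption for each of two subjects, one with 12 seven-day dressings and one with 28 three-day dressings.

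| Version | 12 dressings | 28 dressings | Difference |
|---|---|---|---|
| Protocol | 84/12 = 7.00 | 84/28 = 3.00 | 4.00 |
| Literal | 60/12 = 5.00 | 60/28 = 2.14 | 2.86 |
| Converted | 83/12 = 6.92 | 83/28 = 2.96 | 3.95 |

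Equal interruptions still shrink the literal contrast by 1 − 2.86/4.00, about 29%.

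**The case against.** The best defence is that the error is conditional. Item 26 names no unit and does not cite item 40, and the hours-plus-days form of item 40 suggests that interruptions are recorded in both units. A competent programmer might convert without being told. Other SAP formulas are plainly shorthand: item 9 omits brackets around the date difference in age, and item 11 puts the onset date before the randomization date. A wear time of −17 days would be noticed, and SAP 4.11 plans outlier checks on this regression. Wear time is exploratory and does not enter the derivation of the primary, key secondary or secondary endpoints.

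Most of this stands, and it limits the size of the point. It does not remove the point. The SAP nowhere instructs the conversion. A score of 4 in place of 7, or a subject mean of 5.00 in place of 7.00, is plausible enough to pass an outlier check, and the bootstrap fallback in SAP 4.11 cannot repair wrong inputs. The conflict of definition remains after any conversion.

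It is also fair to say that dropping the interruption term is more than a unit correction, because it settles which quantity is analysed. The reason for doing so is that the protocol and the SAP's own endpoint section already define wear without it.

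**Conclusion.** Wrong as written, with minor impact. Item 26 mixes hours and days in two formulas and contradicts protocol 9.4 and SAP 2.3.3. The distortion arises only for dressings with a recorded interruption, and reaches the sizes shown only if the formula is programmed literally. All interruption lengths are assumed.

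A reader might infer four stronger things that the documents do not support:

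- **That the trial's wear times will be negative.** This depends on programming and on interruptions of unknown frequency and length.
- **That subjects would be wrongly removed from the Per Protocol population.** Subtracting too much shortens wear, so the error can only suppress a flag for more than 7 or more than 3 days. It could hide a deviation and leave a subject in. Even that is conditional: SAP 4.6 does not cite item 26, and neither document says which deviations are significant.
- **That the SAP as a whole defines a different endpoint from the protocol.** SAP 2.3.3 agrees with the protocol; item 26 is the outlier.
- **That the converted values are the right ones.** Under the protocol definition, a 7-day dressing is 7 days whatever the interruption.

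Nor do the documents say that interruptions differ by device. The between-arm illustration does not assume it.

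**What to change.** In SAP 4.3 item 26, delete the interruption term from both formulas that carry it: the one for no unscheduled visit and the one for the dressing after an unscheduled visit. State the unit as days, and cross-refer to SAP 2.3.3 and protocol 9.4. Say in SAP 4.6 that the wear-time deviation flags use this value.

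If time on therapy is also of interest, add it as a separately named derived variable: date difference minus item 40 divided by 24. Where an unscheduled visit splits an interval, state to which dressing the interruption is assigned.

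The cost is an edit to two formulas, a unit statement and a cross-reference, with matching programming. No new data are needed. The one real choice is that the endpoint then measures calendar wear, including time with therapy off, which is what the protocol and SAP 2.3.3 already specify.

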This document contains confidential information, which is the property of Smith & Nephew, Inc. Do not copy, disclose, or circulate without written authorization from the appropriate Smith & Nephew personnel

CONFIDENTIAL DOCUMENT
This document contains confidential information, which is the property of Smith & Nephew, Inc. Do not copy, disclose, or circulate without written authorization from the appropriate Smith & Nephew personnel.

5. Remove NPWT topical dressing to assess the target ulcer.
6. Assess level of pain, post NPWT dressing removal, using the VAS.
7. Complete reason for dressing change assessment and record any additional dressing changes since previous assessment as an unscheduled visit.
8. Assess target ulcer and record if target ulcer is closed or if target ulcer is ready for and will be surgically closed.

Note 1: If the target ulcer is closed, skip procedures 9-15 and complete procedure 16.

Note 2: If target ulcer is ready for and will be surgically closed, skip procedures 9-16 and complete procedure 17.

9. Examine the ulcer for evidence of infection, and treat the infection as appropriate per local protocol.
10. Debride the ulcer if indicated, at the discretion of the Investigator.
11. If the target ulcer remains open, photograph and determine the post-debridement ulcer area (cm²), perimeter (cm), greatest depth (mm), volume (cm³), and maximum linear dimension (cm) using the ARANZ Silhouette wound imaging and measurement device if applicable.

If debridement is not performed, an image of the target ulcer is still required to determine the ulcer area (cm²), perimeter (cm), greatest depth (mm), volume (cm³) and maximum linear dimension (cm) using the ARANZ Silhouette wound imaging and measurement device.

12. Conduct an ulcer assessment using the modified Bates-Jensen wound assessment tool and record percentage tissue type/condition of peri-wound skin assessment (Normal, Erythematous, Edematous, Eczematous, Excoriated, Macerated, Indurated).
13. Re-application of investigational product (PICO) or comparator tNPWT system

according to randomization schedule.

Record any additional dressings used and rationale for using this dressing.

Type of wound filler dressing if used (foam or gauze-based filler dressing).

Number of personnel used to apply NPWT system.

Time used to apply NPWT system (minutes).

Record level of negative pressure, intensity setting and delivery mode selected for tNPWT subjects, if appropriate for device selected.

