9.1.7 Unscheduled Visits

Unscheduled exams may be conducted at the discretion of the Investigator with all obtained information recorded in the source documents and on the Unscheduled Visit pages within the Case Report Form (CRF) booklet.

Subjects using a negative pressure filler dressing or using tNPWT will be instructed to complete a dressing change in 2-3 days from application. This visit should be captured as an unscheduled visit.

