2.3.3 EXPLORATORY ENDPOINTS

The exploratory endpoints are as follows:

Assessment of change in target ulcer progression parameters over the 12-weeks and comparison between treatments including: Estimation of the types of tissue present on the target ulcer, Presence of Infection/Clinical signs of infection, Condition of peri-wound skin, Need for administration of antibiotics and additional interventions, dressing wear time, pain on removal of dressing and at initiation of, and during, therapy.

- The subject's target ulcer will be assessed by the Investigator at each study visit. Where possible this assessment will be made using a modified Bates-Jensen wound assessment tool, this will include information concerning presence of Undermining, Necrotic Tissue Type and Amount, Exudate Type and Amount, Granulation Tissue and Epithelialization. Otherwise the Investigator's assessment against a custom descriptive scale will be used.

Document Number:	1004313	Document Part:	000
Document Version:	06	Document Status:	Released

ST:

9

7

5

Reference:

CE/052/PIC

Customer Code:

0

5

- Condition of peri-wound skin will be assessed by the Investigator against a custom 7-category descriptive scale: Normal, Erythematous, Edematous, Eczematous, Excoriated, Macerated and Indurated. Presence of each skin type will be recorded.
- Assessment of the presence of infection and clinical signs of infection will be undertaken by the Investigator.
- Presence of Undermining, Necrotic Tissue Type and Amount, Exudate Type and Amount, Granulation Tissue and Epithelialization will be assessed using the modified Bates Jensen wound assessment tool.
- Pain associated with removal of dressing, and at initiation of, and during, therapy will be assessed using the Pain VAS scale.
- The need for administration of antibiotics and additional interventions in the opinion of the Investigator will be recorded.
- The duration of dressing wear (dressing wear time) will be calculated using the visit date captured on the CRF and, if applicable, the date of additional/unscheduled dressing changes; by subtracting the date of dressing application from the date of dressing removal. The average wear time will then be derived for each subject using the sum of duration of wear for the subject and the number of dressings utilized by the subject.

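### SAP item 26 ends a wear period at any unscheduled visit, not only at a dressing change, so a visit without a change would lower a subject's average dressing wear time

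*SAP*

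**What the plan says.** Two definitions of dressing wear time stand in the documents.

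- **Endpoint definition.** Protocol 9.4 derives wear "by subtracting the date of dressing application from the date of dressing removal". SAP 2.3.3 uses the visit date and, "if applicable, the date of additional/unscheduled dressing changes". Both obtain the subject's average by dividing total wear by the number of dressings used.
- **Derivation rule.** SAP 4.3 item 26 states: "If an unscheduled visit takes place between consecutive assessments multiple duration of wear values will be derived". The first piece is "Duration of wear 1= Date of unscheduled visit – Date of application study visit". Later pieces run on from the unscheduled visit. No condition refers to a change of dressing. Item 27 then takes "Sum of duration of dressing wear (dressing level) values / Count of duration of dressing wear (dressing level) values".

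Three further statements bear on what an unscheduled visit is. Protocol 9.1.4 tells sites to "record any additional dressing changes since previous assessment as an unscheduled visit", and 9.1.7 has the instructed change at 2–3 days (filler dressings or tNPWT) captured in the same way. Protocol 9.1.7 also says: "Unscheduled exams may be conducted at the discretion of the Investigator", with the information entered on the Unscheduled Visit pages. SAP item 31 reads: "If an unscheduled visit is recorded, where the reason for intervention is not given as routine: Intervention = Yes", so the SAP expects these visits to have differing reasons.

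The derived wear is used twice: in the linear regression on average wear per subject (SAP 4.11), and in the SAP 4.6 deviation examples, which list wear over 7 days for PICO without filler and over 3 days for ActiV.A.C. or PICO with filler.

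**The concern.** Every extra dressing change is recorded as an unscheduled visit, but nothing says that every unscheduled visit is a dressing change. Item 26 treats the two as the same. If a subject is seen between weekly visits and the dressing stays on, a programmer following item 26 would close one wear period and open another for the same dressing. Item 27 would then add one to the denominator and nothing to the total. For that subject the error can go only one way: average wear falls.

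At stake are the wear-time comparison between arms, which is formally modelled, and the completeness of the over-long-wear deviations, since a split can turn one long wear into two that each pass the limit.

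**Working it through.** The documents state no expected wear-time result for this trial, so there is no planned figure to reproduce. The check asks how far item 26 moves a known true wear.

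**Inputs**
- T = 84 days of treatment (SAP 2.3.5).
- True wear: 7 and 6 days, the maximum kit use for low and moderate exudate (Protocol 6.2); 4.6 days, the mean in the proof-of-concept study (Protocol 4.2); 3 days, the upper end of the 2–3 day instruction (Protocol 9.1.7); and 3.5 days, two dressings a week.
- u = unscheduled visits without a change in 84 days. The documents give no rate; 1, 2 and 4 are assumed.
- Therapy interruption, which item 26 subtracts, is set to zero.

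**Average wear.** With c = T / true wear, the true average is T/c. Items 26 and 27 give T/(c + u), a proportional loss of u/(c + u).

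| True wear (days) | c | u = 1 | u = 2 | u = 4 |
|---|---|---|---|---|
| 7 | 12 | 84/13 = 6.46 (−7.7%) | 84/14 = 6.00 (−14.3%) | 84/16 = 5.25 (−25.0%) |
| 6 | 14 | 5.60 (−6.7%) | 5.25 (−12.5%) | 4.67 (−22.2%) |
| 4.6 | 18.3 | 4.36 (−5.2%) | 4.15 (−9.9%) | 3.77 (−18.0%) |
| 3.5 | 24 | 3.36 (−4.0%) | 3.23 (−7.7%) | 3.00 (−14.3%) |
| 3 | 28 | 84/29 = 2.90 (−3.4%) | 84/30 = 2.80 (−6.7%) | 84/32 = 2.62 (−12.5%) |

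**Difference between arms, same u in both**
- PICO 7 days, tNPWT 3 days: true difference 4.0; derived 3.56, 3.20 and 2.62 for u = 1, 2 and 4.
- PICO 4.6 days, tNPWT 3 days: true difference 1.6; derived 1.46, 1.35 and 1.15.
- Both 3.5 days (for example PICO with filler): true and derived difference 0.

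**Unequal u.** With 7-day PICO wear and u = 2, PICO loses 1.0 day. A 3-day tNPWT arm loses as much at 14 such visits, since 84/(28 + 14) = 2.0. With 4.6-day PICO wear and u = 2 the loss is 0.45 day, matched by about 5 tNPWT visits. Beyond those counts the direction reverses.

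**Deviation flags.** All whole-day placements within one interval were enumerated. The ±1 day visit window (Protocol 9.1.4) makes an 8-day interval possible.

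| Flag | Situation | Over-long wear hidden |
|---|---|---|
| >7 days | 8-day wear, one no-change visit | 7 of 7 placements |
| >7 days | 9-day wear, one no-change visit | 6 of 8 |
| >7 days | 14-day wear, one no-change visit | 1 of 13 |
| >3 days | 7-day wear, one no-change visit | 0 of 6 |
| >3 days | 6-day wear, one no-change visit | 1 of 5 |
| >3 days | 7-day interval, one real change, one no-change visit | 12 of 30 |
| >3 days | 7-day wear, two no-change visits | 6 of 15 |

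In the fourth row, any split of 7 days into two leaves a piece of at least 4 days, so the flag still fires.

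**The case against.** The best reply is that item 26 uses unscheduled visit as shorthand for an extra dressing change. Its opening line concerns each individual dressing, SAP 2.3.3 already contains the right rule, and the protocol makes the unscheduled visit the record for extra changes. If every visit entering the derivation is a change, there is no error. That reading is plausible, but item 26 does not state it, and 9.1.7 puts discretionary exams on the same pages.

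The reply is stronger against four wider conclusions that a reader might draw.

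- **That 9.1.7 describes visits with the dressing left on**, such as an adverse-event check or a device alarm. It says only that exams are at the investigator's discretion. No section describes a no-change visit or gives its frequency.
- **That the PICO arm is understated more.** This needs similar no-change visit rates and longer PICO wear. Protocol 6.2 allows PICO with filler, and 9.1.7 gives filler users the same change instruction as tNPWT. The filler share is not given.
- **That over-long wear is generally hidden.** The enumeration shows that it can be, not that it usually is. Missed and out-of-window visits are also listed separately in SAP 4.6.
- **That the primary analysis is affected.** Significant deviations remove subjects from the Per Protocol Population, on which the primary analysis is run, but the documents do not class over-long wear as significant.

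**Conclusion.** The point stands in limited form. Item 26, as written, conflicts with the endpoint definition in Protocol 9.4 and SAP 2.3.3, and can only lower average wear for a subject seen between visits without a dressing change. On the assumed 1 to 4 such visits in 84 days, the understatement is 7.7% to 25.0% for a 7-day dressing and 3.4% to 12.5% for a 3-day dressing. These sizes illustrate the mechanism and do not predict the trial's data.

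At similar visit rates, with PICO worn longer without filler, the effect is to shrink a PICO wear-time advantage. The documents do not settle whether those conditions hold. An 8-day PICO wear without filler is the clearest case of a flag being missed. The consequence is confined to an exploratory endpoint and a deviation summary, so this is a minor correction.

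**What to change.** - In SAP 4.3 item 26, replace unscheduled visit with unscheduled visit at which the dressing was changed, and use the removal and application dates for that change. Other unscheduled visits should not split wear.
- In item 27, count dressings on the same basis, so that the denominator is the number of dressings used, as in Protocol 9.4 and SAP 2.3.3.
- Derive the SAP 4.6 wear flags from the corrected variable.
- Confirm that the CRF's unscheduled-visit page identifies a dressing change. The protocol synopsis lists the number of dressing changes and their reasons as a variable, so this should be available, but the CRF is a separate document and was not seen.

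The cost is one condition in the derivation. If the CRF cannot tell a change from an exam, a field would have to be added or the limitation stated.
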